Study Description:	Colorectal cancer arises from the mucosal layer of the colon. Current screening is performed by flexible endoscopy, which involves visual inspection of the mucosal lining of the colon and rectum with an optical camera mounted on the endoscope, with abnormal areas being biopsied. This method is somewhat limited in that there are no readily available surface pattern or morphological classification systems with adequate sensitivity or specificity to evaluate extent of submucosal invasion (deep, superficial, or none). Optical coherence tomography (OCT) using pattern recognition is a high-resolution imaging modality. There is currently an unmet need to predict depth of invasion for colonic tumors to decide on applicability of endoscopic (endoscopic submucosal dissection or endoscopic mucosal resection) vs. surgical therapy. Our hypothesis is that OCT will have a higher diagnostic accuracy for determining depth of submucosal invasion compared to existing modalities. We will first aim to assess the procedural feasibility and safety of using an OCT probe during routine colonoscopy with an early feasibility study. This study will identify appropriate modifications to the device and help with development of subsequent clinical study protocols. The eventual goal is to assess the diagnostic accuracy of OCT imaging for predicting depth of invasion of colonic tumors.
Objectives:	
Primary Objective: To demonstrate the procedural feasibility of OCT during routine colonoscopy.
 
Secondary Objective:
 
 • To describe the safety of the OCT probe during routine colonoscopy. • To evaluate the quality of OCT images using a machine learning algorithm. • To explore the diagnosis agreement between OCT imaging and pathology when a lesion is biopsied.
Endpoints:	
Primary Endpoint: Whether a lesion can be adequately evaluated with OCT within 5 minutes during a standard of care colonoscopy.
 
Secondary Endpoints:
 
 • Adverse events related to OCT imaging during routine colonoscopy. • Whether OCT image is successfully captured using machine learning algorithm.

	
 Weighted kappa
Study Population:	Fifty-four adults undergoing standard of care colonoscopy for the evaluation of colonic polyps will be enrolled in this study.
Phase:	N/A
Description of Sites / Facilities Enrolling:	This study will enroll patients at Washington University School of Medicine.
Description of Study Intervention:	The OCT probe (Section 12, Figure 1) is attached to an approximately 3-meter wire that is attached to the OCT fiber probe system setup. This setup consists of a power supply unit, and a control platform that controls fiber probe rotation and retraction. The OCT probe will be advanced through the colonoscope instrument channel (Section 12, Figure 2).
Study Duration:	12 months (enrollment) + 1 day (participation) + 2 days (follow-up) + 6 months (analysis)
Participant Duration:	3 days

1.0 INTRODUCTION

1.1 Study Rationale

Endoscopic submucosal dissection (ESD) and endoscopic mucosal resection (EMR) are used to treat superficial colorectal neoplasms but are contraindicated by deeply invasive colorectal cancer. Estimating depth of invasion is crucial to guiding treatment strategies. Current methods for estimating this depth are not readily available, expensive, or lack accuracy. There have been no *in vivo* studies using optical coherence tomography to differentiate between different types of polyps. We would like to determine the procedural feasibility and safety of using an optical coherence tomography (OCT) probe for evaluation of colonic polyps during routine colonoscopy.

If this feasibility study is successful we will then plan a study of patients with large complex polyps referred for EMR or ESD to Washington University, where we would evaluate the accuracy of the OCT probe for determining depth of submucosal invasion.

1.2 Background

1.2.1 Colonoscopy Polyp Detection Rate and Adenoma Detection Rate

Guidelines support performance targets for adenoma detection rate of 25% for a mixed gender population (20% in women and 30% in men). Polyp detection rate (PDR) and adenoma detection rate (ADR) increase with age, with one study showing a PDR/ADR ratio of 16.9%/6.3% for patients in their 20s, 33%/14.0% for patients in their 30s, 43.5%/28.7% for patients in their 40s, 54.3%/38.4% for patients in their 50s, 61.2%/46.2% for patients in their 60s, 68.7%/55.8% for patients in their 70s, and 65.9%/56.1% for patients in their 80s ($P < 0.001$) [1]. Polyp detection rate is relevant for patient selection. Because we want to maximize the chance that a patient will have a polyp (hyperplastic, adenoma, etc.) that OCT can image, inclusion criteria will include age 40 years or older.

1.2.2 Diagnostic Accuracy of Depth of Invasion

Being able to differentiate between deep ($> 1\text{ mm}$) and superficial ($< 1\text{ mm}$) submucosal is a crucial branch point in clinical decision making. Deep submucosal invasion carries an 8-23% risk of lymph node metastasis. These lesions should be referred to surgery. On the other hand, if a lesion has superficial submucosal invasion and the endoscopist completes "en bloc" resection with EMR or ESD, then this is considered curative. While NICE 3 classification (Section 12, Figure 3) has up to a 94% accuracy for lesions with deep submucosal invasion, there are no readily available surface pattern or morphological classification systems with adequate sensitivity or specificity for superficial submucosal invasion [2]. Increasing diagnostic accuracy for lesions with superficial submucosal invasion would aid in the decision-making process of whether or not to refer a patient with a suspicious polyp to colorectal surgery or for endoscopic therapy.

Current options for estimation of invasion depth include gross features on endoscopy, narrow band imaging, magnifying chromoendoscopy, endoscopic ultrasonography, endocytoscopy, and confocal laser endomicroscopy. The only modality in widespread use is narrow band imaging, which does not require the use of magnification or dye spray.

Narrow band imaging using the NICE classification is limited in identifying superficial submucosal invasion. JNET (Section 12, Figure 4) was formed to help better differentiate between low grade intramucosal neoplasia and superficial submucosal invasion. This classification has an accuracy of <80% for lesions with superficial submucosal invasion and requires magnifying chromoendoscopy, which is not readily available [3]. Endoscopic ultrasonography is comparable to magnifying chromoendoscopy with neither modality having sufficient diagnostic accuracy for depth of invasion [4].

1.2.3 Optical Coherence Tomography (OCT)

In prior work, several research groups have demonstrated promising results that suggest OCT, an established high resolution imaging modality [5,6,7], may address the shortcomings of traditional camera endoscopy in the upper gastrointestinal tract [8,9,10] or large intestine [11,12,13]. OCT has been shown to accurately differentiate abnormal from normal tissue in multiple organs as an “optical biopsy” tool [14,15,16] in both murine and human colorectal models [17,18,19,20]. However, clinical application of the technology is complicated by the large volume of data generated and the subtle qualitative differences between normal and abnormal tissue.

The success of convolutional neural networks (CNN) in computer vision tasks has popularized deep learning for CAD imaging [21,22,23]. CNNs have successfully been applied to OCT images for ophthalmological, esophageal, and cardiac diseases [24,25,26]. Moreover, CNN has also been applied to colon cancer diagnostics in an image classification [27,28,29].

The [name] lab reported the use of pattern-recognition OCT(PR-OCT) in differentiating normal from neoplastic colorectal tissue (Section 12, Figure 5). Using RetinaNet, a novel neural network architecture for pattern recognition tasks, a dentate structural pattern was used as a structural marker of normal specimens and in PR-OCT prediction. This method leverages the recent advancement in object detection, which localizes and classifies the diagnostic features at real-time, and achieves an accurate classification result. This initial study demonstrated the feasibility of using PR-OCT as an “optical biopsy” tool to assist physicians in real-time for mucosal neoplasms screening [30].

The current OCT system developed by [name] et al has so far been tested on a limited number of specimens in an ex-vivo study using specimens collected after surgical

resection (16 normal, 2 adenomatous polyps, 4 treated areas (2 complete responders, 2 non-responders). Using OCT and training this input with deep learning, the [name] lab achieved a sensitivity and specificity of 100% and 99.7%, respectively for normal vs cancerous tissue in an ex-vivo model.

Currently, there are limited studies that focus on determining sensitivity and specificity of OCT for evaluation of different types of polyps. Further, there are no studies using this technology in real time for colorectal cancer screening.

1.3 Study Design

1.3.1 Overall Design

This is a one-arm non-blinded study to investigate the feasibility of an OCT probe for the patients undergoing routine screening or surveillance colonoscopy. Time added to length of overall procedure will serve as a surrogate endpoint towards evaluating ease of procedure for the endoscopist and endoscopy staff. We expect to find polyps in the enrolled patients. One polyp per patient will be imaged. A population of patients undergoing routine colonoscopy on the 8th floor of Center for Advanced Medicine will be targeted. The duration of each patient's participation will last from the time of screening to 48 hours after the colonoscopy to evaluate for adverse events.

Patients will be screened for the study prior to undergoing routine colonoscopy. The OCT probe system setup will be placed in a pre-determined room in the GI endoscopy suite on 8th floor of Center for Advanced Medicine. Once a polyp is found (hyperplastic, adenoma, or malignant appearing), the OCT probe will be advanced through the channel of the colonoscope. Image capture is expected to take around 3 minutes. We will have a goal of imaging one polyp per patient. If no polyps are found then the OCT probe will be used to image an area of normal colonic mucosa.

1.3.2 Scientific Rationale for Study Design

Our goal is to assess feasibility of using OCT probe during routine colonoscopy. Therefore, we are going to screen patients 40 years of age or older for inclusion in this study because these patients have a higher chance of having polyps that can be imaged. Because we are assessing the feasibility of a new device, there will be no blinding or randomization. The secondary objective of correlating OCT images with pathology is exploratory in nature.

1.4 Risk/Benefit Assessment

1.4.1 Known Potential Risks

Known potential risks include added procedure sedation time as a result of OCT

imaging. We expect each polyp to be imaged within the span of 3 minutes and do not expect adding more than 5 minutes to total procedure time. Risk of infection and bleeding is <1% in standard of care colonoscopy. We don't expect the OCT probe to increase these risks. A table of common adverse events during a routine colonoscopy (with rates in percentages) is presented below. Adverse event rates in this study will be compared to the historic AE rates from this table.

Adverse Events 30 days After Outpatient Screening or Follow-Up Colonoscopy [31]

	Screening	Surveillance	No Polypectomy	Polypectomy
Death	0.03%	0.06%	0.02%	0.05%
Perforation	0.04%	0.12%	0.03%	0.07%
Hemorrhage	0.27%	0.38%	0.08%	0.50%
Diverticulitis	0.18%	0.22%	0.18%	0.20%
Abdominal pain	2.64%	2.21%	2.62%	2.56%
Any serious adverse event*	0.47%	0.68%	0.27%	0.74%
Hospitalizations	1.11%	1.61%	0.94%	1.43%
Emergency Department or Urgent Care Visit	2.26%	3.01%	2.23%	2.47%

*Serious adverse events include perforation, hemorrhage, or diverticulitis.

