5.0 STUDY PROCEDURES

5.1 Recruitment

Adult patients scheduled to undergo a routine colonoscopy for screening or surveillance of colon polyps, evaluation of GI bleeding, post-colon cancer resection surveillance, or reassessment of prior colon polyp will be screened for the study. Patients will be identified as candidates for the study from the BJH Surgery schedule the day before they come in. One of the investigators or a research assistant will discuss the study with potential participants in the pre-endoscopy area. Those subjects who qualify for the study based on eligibility criteria will be invited to participate. The consent process will take place in the

pre-endoscopy area. Those patients who wish to participate will sign the informed consent document and proceed to colonoscopy.

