5.3 Definitions of Evaluability

A patient must have had at least one colonic polyp or area of normal mucosa selected for OCT imaging in order to be evaluable for the feasibility endpoint. Any patient who does not have any area of mucosa imaged by OCT (either due to poor bowel prep, anesthesia complications, etc.), will be considered inevaluable for the feasibility endpoint and will be replaced.

All patients who undergo colonoscopy using the OCT probe are evaluable for toxicity and evaluation of imaging quality. Patients are evaluated for AEs from time of colonoscopy until 48 hours after colonoscopy.

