6.0 REGULATORY AND REPORTING REQUIREMENTS

The entities providing oversight of safety and compliance with the protocol require reporting as outlined below. Please refer to Appendix A for definitions and Appendix B for a grid of reporting timelines.

Adverse events will be tracked from time of colonoscopy through 48 hours after end of colonoscopy. All adverse events must be recorded on the toxicity tracking case report form (CRF) with the exception of:

- Baseline adverse events, which shall be recorded on the medical history CRF

Refer to the data submission schedule in Section 7 for instructions on the collection of AEs in the EDC.

Reporting requirements for Washington University study team may be found in Section 6.1.

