10.5.4 Endpoint Analysis

Proportions of the patients whose procedure length using an OCT probe during routine colonoscopy is within 5 minutes and who have good OCT images, as judged by a machine learning algorithm, will be provided. Their associated 95% confidence intervals (CIs) will be calculated assuming a binomial distribution. The descriptive statistics will be presented including frequency, type, and severity of AEs related to OCT imaging during routine colonoscopy. Weighted kappa and 95% CI will be computed for the agreement between OCT imaging and pathology for all enrolled patients. All analyses will be conducted using SAS (SAS Institute, Cary, NC) at the two-sided 5% significance level.

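### Section 1.4.1 sets 48-hour adverse event rates from this study against a table of 30-day rates, and nothing in the plan reconciles the two windows

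*Combined protocol and SAP*

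**What the plan says.** Section 1.4.1 presents a table of adverse event rates after colonoscopy and commits the study to using it: "Adverse event rates in this study will be compared to the historic AE rates from this table". The table is headed "Adverse Events 30 days After Outpatient Screening or Follow-Up Colonoscopy". The footnote to its serious-event row reads: "Serious adverse events include perforation, hemorrhage, or diverticulitis".

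The study's own window is 48 hours wherever it is set:

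- Section 1.3.1: participation runs "from the time of screening to 48 hours after the colonoscopy to evaluate for adverse events".
- Section 5.3: "Patients are evaluated for AEs from time of colonoscopy until 48 hours after colonoscopy".
- Section 6.0: "Adverse events will be tracked from time of colonoscopy through 48 hours after end of colonoscopy".
- The protocol summary (2 days of follow-up), the phone call in Section 5.2, the toxicity form schedule in Section 7.0 and the schedule of activities in Section 8.0 all agree.

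For the analysis, Section 10.5.4 says: "The descriptive statistics will be presented including frequency, type, and severity of AEs related to OCT imaging during routine colonoscopy". It gives 95% confidence intervals for the feasibility proportion, the image-quality proportion and the weighted kappa, but not for adverse event rates. Section 10 does not mention the historical comparison.

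**The concern.** An event on day 5 counts in the historical rate but cannot count in the study rate. With event type, population and ascertainment held fixed, the shorter window can only lower the study's count or leave it unchanged. A finding that study rates were at or below historical rates could therefore arise from the window alone.

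Section 1.4.1 also does not say which study events enter the comparison. All adverse events are recorded under Sections 6.0 and 7.1, but Section 10.5.4 summarises only those related to OCT imaging. The table's heading carries no such restriction. If the OCT-related set were used, the study count would fall further.

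Safety is the first secondary objective listed, and the study is meant to inform later protocols. What is at stake is an apparently reassuring safety statement that the design cannot support.

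**Working it through.** The plan gives no figure for this comparison, so there is none to reproduce. The check has three parts.

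**1. The two sides of the comparison**

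| | Table in 1.4.1 | This study |
|---|---|---|
| Window | 30 days | 48 hours |
| Serious event | Perforation, hemorrhage or diverticulitis | Appendix A: also death, life-threatening events, hospitalization, other important medical events |
| Events covered | Heading not limited to device-related events | All recorded; only OCT-related summarised in 10.5.4 |
| Patients | Outpatient screening or follow-up | Section 5.1 also takes "evaluation of GI bleeding, post-colon cancer resection surveillance, or reassessment of prior colon polyp will be screened for the study" |

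No passage restricts the historical rates to 48 hours, plans a later contact or chart review for adverse events, or warns that the windows differ.

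**2. What 54 patients can show, even at the full 30-day rates**

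Inputs: N = 54 (Section 10.3) and the rates in the Section 1.4.1 table. Expected count = 54 × rate; P(none) = (1 − rate)^54.

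- Serious events: 54 × 0.0027 = 0.15 and 54 × 0.0074 = 0.40. P(none) = 0.9973^54 = 0.864 and 0.9926^54 = 0.670.
- Serious events at three times those rates: 0.9919^54 = 0.645 and 0.9778^54 = 0.298. At the upper rate, exactly one event has probability 54 × 0.0222 × 0.9778^53 = 0.36.
- Hospitalizations: 54 × 0.0094 = 0.51 to 54 × 0.0161 = 0.87.
- Abdominal pain: 54 × 0.0221 = 1.19 to 54 × 0.0264 = 1.43.
- Emergency department or urgent care visits: 54 × 0.0223 = 1.20 to 54 × 0.0301 = 1.63.
- Exact (Clopper-Pearson) two-sided 95% upper limit: 0/54 gives 1 − 0.025^(1/54) = 6.60%. 1/54 gives 9.89%, the solution of (1 − p)^54 + 54p(1 − p)^53 = 0.025. The largest rate in the table is 3.01%.

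**3. How much the window could remove**

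The documents do not give the share of 30-day events that fall within 48 hours. The shares below are assumptions, applied to the highest serious-event rate and the highest rate in the table.

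| Assumed share within 48 hours | Expected serious events (0.74%) | P(none) | Expected ED or urgent care visits (3.01%) | P(none) |
|---|---|---|---|---|
| 100% | 0.40 | 0.67 | 1.63 | 0.19 |
| 75% | 0.30 | 0.74 | 1.22 | 0.29 |
| 50% | 0.20 | 0.82 | 0.81 | 0.44 |
| 25% | 0.10 | 0.90 | 0.41 | 0.67 |

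For the commonest row, the window could move the chance of seeing no event from 19% to 67% with no change in true risk.

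**The case against.** The strongest case is that this is a wording matter. The safety objective is only descriptive, the sample size rests on feasibility alone, and the stopping rule in Section 10.6 uses 5% and 30%, not this table. The comparison appears once, in the risk/benefit background. That stands, and it limits the harm to interpretation.

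A second objection is that the window effect is small beside sampling noise. It can remove at most 0.40 expected serious events and about 1.6 emergency or urgent care visits, and 54 patients would be uninformative for rare events even with matched windows. This is right as far as it goes. The imprecision is a separate weakness from the mismatch, but it adds to the case against presenting the comparison as evidence of safety.

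Third, the overall direction is not settled. Appendix A's broader serious-event definition and the wider recruitment in Section 5.1 could raise the study's rate. The 48-hour phone call might too, although the documents do not say how the historical source ascertained its events. This stands: only the window's own effect has a known sign. These differences do not rescue the comparison; they are further ways in which the two sets of rates fail to match.

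Fourth, all-cause events are not lost, because Section 9.0 puts a toxicity summary in the semi-annual monitoring report. True, but that is not a planned analysis with intervals.

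Finally, exact intervals go beyond the mismatch itself. Deleting or qualifying the sentence does cure the contradiction. The intervals supply what the comparison was presumably meant to provide.

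**Conclusion.** The concern holds. Section 1.4.1 promises a comparison with 30-day rates, every passage that sets the study's window stops at 48 hours, and nothing reconciles them. The window taken alone favours the probe; the size and sign of the net bias cannot be derived from the documents.

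For serious events, none is the likeliest result at the table's rates (86% to 67%). At three times those rates the chance of none is still 64% to 30%, although at the upper end a single event is slightly likelier than none. These probabilities assume 54 independent patients and the full 30-day rates; any share of events falling after 48 hours raises the chance of none. Zero events in 54 would leave rates up to 6.6% within the exact 95% interval.

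The plan should be corrected, but the point does not touch the primary endpoint, the sample size or the stopping rule.

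**What to change.** In Section 1.4.1, delete the sentence promising the comparison. Alternatively, keep the table as context only and state that its 30-day window and its three-event definition of serious differ from the study's 48 hours and from Appendix A.

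In Section 10.5.4, add:

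> The number and proportion of patients with at least one AE and with at least one SAE within 48 hours, all-cause and OCT-related, will be reported with exact 95% CIs among all patients in whom the OCT probe was used.

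Note beside it that with no event in 54 patients the upper limit is 6.6%.

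The cost is a few lines of text and intervals on data already collected under Sections 6.0 and 7.1. No follow-up, visit, record access or patient is added, and no clinical rule changes. The price is a more modest safety statement.

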1.4.2 Known Potential Benefits

There is no direct benefit to the patient. We hope that this feasibility study will answer the question of whether or not this OCT probe is feasible in routine colonoscopy. This may lead to another study of assessing the diagnostic accuracy of the OCT probe.

1.4.3 Assessment of Potential Risks and Benefits

OCT is an older technology used by many research groups and commercially in eye clinics. The probe is made by [name] lab. We anticipate that the potential benefits outweigh the minimal risks.

2.0 OBJECTIVES AND ENDPOINTS

Objectives	Endpoints
Primary	
To demonstrate the procedural feasibility of OCT during routine colonoscopy	Whether a lesion can be adequately evaluated with OCT within 5 minutes during a standard of care colonoscopy.
Secondary	
To describe safety of OCT probe during routine colonoscopy	Adverse events related to OCT imaging during routine colonoscopy
To evaluate the quality of OCT images using a machine learning algorithm.	Whether OCT image is successfully captured using machine learning algorithm
To explore the diagnosis agreement between OCT imaging and pathology when a lesion is biopsied.	Weighted kappa

